9.2.4. NeuroQOL Response

NeuroQOL is a set of self-report measures that assesses the health-related quality of life (HRQOL) of adults and children with neurological disorders that includes stroke. The HRQOL domains included in NeuroQOL were identified through several sources, including an extensive literature review, an on-line Request for Information (RFI), two phases of in-depth expert interviews (n=44 and n=89, respectively), subject and caregiver focus groups (N =11 groups) and individual interviews with subjects and proxies (N = 63). On the basis of this input, 17 HRQOL domains and sub-domains were chosen for adults. Given this study's focus on improvements in motor function, two subdomains of the NeuroQOL will be assessed using the Short Forms: Upper Extremity Function and Lower Extremity Function. These two subdomains employ five response options (1 = Unable to do, 2 = With much difficulty, 3= With some difficulty, 4 = With little difficulty, 5 = Without any difficulty) that a respondent can choose from when responding to a question or statement. The total raw score is the sum of the values of the response to each question. For example, for an 8-item form that includes items with 5 response

INC1005439

Sponsor: San-Bio, Inc.

Protocol: SB-STR02

Final 1.0

Statistical Analysis Plan

options ranging from 1 to 5, the lowest possible raw score is 8 (8×1) ; the highest possible raw score is 40 (8×5) . Conversion or look-up tables provided below can then be used to convert the raw scores into a T-score.

Upper Extremity Function – Fine Motor, ADL 8-item Short Form (Adult)					
Raw Score	T-Score	SE	Raw Score	T-Score	SE
8	12.8	2.0	25	27.3	2.0
9	13.7	2.3	26	28.0	2.0
10	14.7	2.4	27	28.7	2.0
11	15.8	2.5	28	29.5	2.0
12	16.9	2.4	29	30.2	2.1
13	18.0	2.4	30	30.9	2.1
14	19.0	2.3	31	31.7	2.1
15	19.9	2.2	32	32.6	2.2
16	20.8	2.1	33	33.5	2.3
17	21.6	2.1	34	34.5	2.4
18	22.4	2.1	35	35.6	2.7
19	23.1	2.0	36	37.1	3.2
20	23.9	2.0	37	39.3	4.2
21	24.6	2.0	38	41.2	4.5
22	25.3	2.0	39	43.7	4.7
23	26.0	2.0	40	53.8	7.8
24	26.7	2.0			

Statistical Analysis Plan

Lower Extremity Function - Mobility 8-item Short Form (Adult)					
Raw Score	T-Score	SE	Raw Score	T-Score	SE
8	16.5	3.0	25	35.2	2.1
9	19.2	2.8	26	36.0	2.1
10	21.1	2.6	27	36.7	2.1
11	22.6	2.4	28	37.5	2.1
12	23.9	2.3	29	38.3	2.1
13	25.1	2.3	30	39.1	2.2
14	26.2	2.2	31	39.9	2.2
15	27.2	2.2	32	40.8	2.3
16	28.1	2.1	33	41.7	2.4
17	29.0	2.1	34	42.8	2.5
18	29.9	2.1	35	43.9	2.6
19	30.7	2.1	36	45.2	2.9
20	31.5	2.1	37	46.7	3.1
21	32.2	2.1	38	48.6	3.3
22	33.0	2.1	39	51.2	3.8
23	33.7	2.0	40	58.6	6.4
24	34.5	2.1			

A score can be approximated if a participant skips a question before calculating the T-score. If items are missing, first check how many items were answered. For short forms with at least 5 items, confirm that 4 or 50% of items, whichever is greater, have been answered. For example, a 4-item short form can only be scored with complete data. A 10-item short form can be scored as long as the participant answered at least 5 items. After confirming that enough responses were provided, sum the response scores from the items that were answered. Multiply this sum by the total number of items in the short form. Finally, divide by the number of items that were answered. For example, if a respondent answered 5 of 8 questions and answered all items with the second lowest response option (2), you would sum all responses (10), multiply by the number of items in the short form (8) and divide by the number of items that were actually answered (5). Here $(10 \times 8) / 5 = 16$. If the result is a fraction, round up to the nearest whole number. This is a prorated raw score. However, this prorated score should be used with caution as the advantages of Item Response Theory (IRT) calibrations and their contribution to precision is lost in the process.

The mean score change from baseline in the two subdomain (Upper extremity function and Lower extremity function) for the T scores of SB623 treated subjects (individually

Statistical Analysis Plan

by treatment group and for both groups combined) will be compared to sham-surgery controls at each timepoint using a mixed model for repeated measures model (MMRM).

Restricted maximum likelihood MMRM model will include treatment, visit, pooled site, corresponding baseline subdomain T score, baseline mRS score, and the treatment-by-visit interaction. The same step-down procedure described in Section 9.1.1 will be used if the unstructured covariance matrix used in the model does not converge. Missing observations will not be imputed for this analysis. Least square mean differences and 95% CIs will be presented for SB623 treatment individual and combined groups versus sham control.

9.2.5. Global Rating of Perceived Change

This assessment will be performed by both subject (may be completed by caregiver) and clinician. Subjects and clinicians will be asked about perceived changes in their motor function by comparing “how well they are doing compared to before the surgical procedure”. The subject global rating of perceived change should be completed by the subject. In the event the subject is not able to complete the questionnaire, the caregiver will be allowed to ask the questions of the subject and complete the questionnaire using the subject’s answer(s). The following 7-point Likert scale will be used:

- 7 = Much better
- 6 = A little better, meaningful
- 5 = A little better, not meaningful
- 4 = About the same
- 3 = A little worse, not meaningful
- 2 = A little worse, meaningful
- 1 = Much worse

The proportion of SB623 treated subjects (pooling both SB623 doses) scoring either 7 (much better) or 6 (a little better, meaningful) on the Global Rating of Perceived Change by both subject and clinician will be compared to sham-surgery controls using a logistic regression model with treatment (SB623 vs. sham control), visit, baseline FMMS motor total score, baseline mRS score, and pooled surgical site as factors. The outcome variable of this analysis is a dichotomized variable based on of the Global Rating of Perceived Change score (≥ 6 vs. < 6). The analysis will be repeated by the comparisons of each SB623 group versus sham control for each visit.

9.3. OTHER EFFICACY ANALYSIS

Graphs will be presented summarizing the LS mean value over time by treatment group (pooled SB623, individual SB623 groups and sham control) for the following variables: change from baseline in FMMS total score, changes from baseline in the two NeuroQOL

INC1005439

Sponsor: San-Bio, Inc.

Protocol: SB-STR02

Final 1.0

Statistical Analysis Plan

subdomain T scores. The graphs will plot the LS mean (\pm standard error) over time. The graphs will also present the p-value at each post-baseline timepoint from the MMRM model comparing each SB623 group with sham control.

The following subgroup analyses will be performed for the primary endpoint:

- Baseline FMMS motor total score: (0 - 34, 35 -67, 68 - 100)
- Baseline FMMS motor total score: (0 - 50, 51- 100)
- Age group: ≥ 55 and < 55 years
- Age group: 18 to < 50 and 50 to 75
- Gender
- Race: White and other races
- Length from the last stroke: 6-12, >12 -24 and >24 months
- Stroke location: Subcortical grey matter; subcortical white matter; cortical frontal; cortical temporal; cortical parietal; cortical other
- Cerebral infarct size: < 50 , 50 - 75, >75 - 100 and >100 -150 cm^3
- Compliance with the physical therapy throughout the study: yes ($\geq 80\%$ of all tasks) or no
- Baseline mRS score: 2, 3 and 4
- The primary efficacy endpoint will also be summarized by viable cell/mL and by percentage cell viability (\leq sample median value vs. $>$ sample median value). These subgroup analyses will be done for the SB623 doses only.

Subgroups with total number of subjects less than 10 will be combined into a single subgroup.

Statistical Analysis Plan

10. SAFETY

All safety data will be summarized descriptively for the Safety Population.

Safety will be assessed on the basis of extent of exposure, AEs, MRI images adverse changes, clinical laboratory tests (chemistry, hematology, and urinalysis), concomitant medications/procedures, 12-lead ECG, vital signs, physical examinations and antidrug antibody.

10.1. EXTENT OF EXPOSURE

Randomized subjects will receive approximately 2.5 million SB623 cells, approximately 5 million SB623 cells or sham surgery on Day 1. Extent of exposure for SB623 will be summarized by presenting total number of cells received, cell viability (viable cells and percent viability), actual deposit volume per track, total deposit volume and duration of surgery. Duration of surgery will be calculated as time of end of last track minus time of start of first track.

Details for the injection records collected in the CRF will be listed for each subject.

10.2. TREATMENT COMPLIANCE

The compliance with the maintenance of the blind will be evaluated by testing whether the surgical time (SB623 pooled versus sham control) is statistically significant using 2 sample t-test.

10.3. ADVERSE EVENTS

All adverse events (AEs) will be collected in the CRF and coded to SOC and PT using the MedDRA coding dictionary version 18.0 or later.

A treatment-emergent adverse event (TEAE) is any untoward medical occurrence that either occurs or worsens at any time on or after surgery and that does not necessarily have to have a causal relationship with the treatment or surgical procedure. Please see Section 7.3.1 for handling missing or incomplete dates in determining whether an AE is a TEAE.

Relationship of the AE to study product or surgery will be recorded as definitely, probably, possibly unlikely and not related. Relationships recorded as definitely, probably or "possibly related" AEs will be considered as related to study product or surgery as described in Table 4 in the protocol.

Severity (Toxicity) of an AE will be recorded as mild, moderate, severe or life-threatening.

A serious AE (SAE) is any AE that results in any of the following:

- Death,

Statistical Analysis Plan

- Life-threatening event,
- Hospitalization or prolongation of hospitalization,
- A persistent or significant disability/incapacity,
- Congenital anomaly/birth defect, or
- An event that may require intervention to prevent any one of the other outcomes listed above (based on medical judgment)

Adverse event leading to discontinuation is any AE that lead to early discontinuation of a subject before the completion of the trial.

Actions taken as a result of an AE will be recorded to the following categories: surgical intervention, concomitant medication introduced, discontinued, or not applicable.

AE outcomes will be recorded as recovered/resolved, recovering/resolving, not recovered/not resolved, recovered/resolved with sequelae, fatal, or unknown. Data will be summarized using counts and percentages. The following summary tables of TEAEs will be produced:

- Overall summary of TEAEs
- TEAEs by SOC and PT
 - All TEAEs
 - TEAEs reported by the surgical site
- TEAEs by PT
- TEAEs by maximum severity, SOC and PT
- TEAEs by maximum relationship to Investigational product, SOC and PT
- TEAEs by maximum relationship to surgical procedure, SOC and PT
- Serious TEAEs by SOC and PT
- TEAEs leading to study discontinuation by SOC and PT
- Listing of deaths

The number and percent of subjects with TEAEs will be presented and sorted by descending frequency of TEAEs in SB623 combined column. The overall number of TEAEs for each treatment group will be summarized in the table for overall TEAEs. A subject will be counted once at each level of summation by SOC or PT. The highest severity (severe > moderate > mild) or relationship with the investigational product or surgery by Related (definitely, probably, possibly) and Not Related (unlikely, not related) will be summarized, where appropriate. Missing severity, seriousness or relationship will be counted as severe, serious or treatment-related, respectively.

All data collected in the CRF will be presented in data listings. SAEs and AEs leading to study discontinuation will be listed separately. TEAE will be indicated in the data listings.

Statistical Analysis Plan

10.4. LABORATORY EVALUATIONS

Clinical laboratory data including serum chemistry, hematology, urinalysis, INR and pregnancy testing will be collected according to the schedule of assessments.

The following summaries for each scheduled visit will be produced:

- Actual value and change from baseline for continuous variables
- Shift from baseline to post-baseline of low/normal/high, normal/abnormal, or negative/positive as well as shift tables from baseline to worst toxicity grade on the study.

All results will be included in data listings with abnormal results flagged. Markedly abnormal post-baseline results will be summarized.

Markedly Abnormal Post-Baseline Laboratory Values (MAPLV) for selected laboratory parameters can be found in Table 3. The criterion of MAPLV is satisfied if a value falls into the markedly abnormal range. Subjects will be represented in the count of a particular MAPLV if they have experienced that MAPLV at least once in the double-blind phase post-Baseline, regardless of Baseline value, up to and including endpoint. The number and percentage of subjects with MAPLV will be presented by treatment group.

Table 3 Criteria for Markedly Abnormal Post-Baseline Laboratory Parameters

Parameter Name Gender	Markedly Abnormal Low	Markedly Abnormal High
Hematology		
WBC	$\leq 2.8 \times 10^3/\text{mm}^3$	$\geq 16 \times 10^3/\text{mm}^3$
Absolute Neutrophils	$< 1.5 \text{ k/mm}^3$	$> 13.5 \text{ k/mm}^3$
Absolute Lymphocytes	N/A	$> 12 \text{ k/mm}^3$
Monocytes	N/A	$> 2.5 \text{ k/mm}^3$
Hemoglobin		
Females	$\leq 9.5 \text{ g/dL}$	$\geq 17.5 \text{ g/dL}$
Males	$\leq 11.5 \text{ g/dL}$	$\geq 19.0 \text{ g/dL}$

INC1005439

Sponsor: San-Bio, Inc.

Protocol: SB-STR02

Final 1.0

Statistical Analysis Plan

Parameter Name Gender	Markedly Abnormal Low	Markedly Abnormal High
Hematocrit		
Females	≤ 32%	≥ 54%
Males	≤ 37%	≥ 60%
Platelet Count	≤ 75 x 10 ³ /mm ³	≥ 700 x 10 ³ /mm ³
Chemistry		
Sodium	≤ 130 mEq/L	≥ 150 mEq/L
Potassium	≤ 3 mEq/L	≥ 5.5 mEq/L
Chloride	≤ 90 mEq/L	≥ 118 mEq/L
Calcium	< 7 mg/dL	≥ 12 mg/dL
AST	N/A	≥ 3 x ULN*
ALT	N/A	≥ 3 x ULN*
Alkaline phosphatase	N/A	> 400 U/L
Creatinine	N/A	> 1.5 mg/dL
BUN	N/A	≥ 30 mg/dL
Total bilirubin	N/A	≥ 2 mg/dL
Total protein	≤ 4.5 g/dL	≥ 10 g/dL
Blood Coagulation		
aPTT	N/A	> 1.5 ULN
INR	N/A	> 1.5 ULN

This document is proprietary and confidential to Syneos Health LLC.

Statistical Analysis Plan

Parameter Name	Markedly Abnormal Low	Markedly Abnormal High
Gender		
Thyroid Function		
Free T3	< 200 pg/dL	> 415 pg/dL
Free T4	< 0.75 ng/dL	> 1.75 ng/dL

Treatment emergent abnormalities will be listed separately. All laboratory data collected will be listed, including the following tests:

- Pregnancy testing
- HLA typing and ApoE4 and BDNF Val66Met Genotyping
- Serum Anti-HLA Antibodies (including MFI values)

10.5. VITAL SIGNS

Oral temperature, blood pressure measured in seated position, pulse rate and respiratory rate will be collected according to the schedule of assessments.

Summary statistics for vital signs will be provided. Vital signs will be summarized by presenting summary statistics of actual data, and change from baseline values (means, standard deviations, medians, ranges). Markedly Abnormal Post-Baseline Vital Signs MAPVS will be summarized. Abnormal values will be flagged in data listings.

Abnormal results are specified as:

- Pulse
 - ≤ 50 bpm and decrease from baseline ≥ 15 bpm
 - ≥ 120 bpm and increase from baseline ≥ 15 bpm
- Systolic BP
 - ≤ 90 mmHg and decrease from baseline ≥ 20 mm Hg
 - ≥ 180 mmHg and increase from baseline ≥ 20 mm Hg
- Diastolic BP
 - ≤ 50 mmHg and decrease from baseline ≥ 15 mm Hg
 - ≥ 105 mmHg and increase from baseline ≥ 15 mm Hg
- Respiratory Rate
 - ≤ 8 breaths/min and decrease from baseline 20%
 - ≥ 20 breaths/min and increase from baseline 20%

Statistical Analysis Plan

- Body Temperature
 - $\geq 38.3^{\circ}\text{C}$

10.6. ECG

All ECGs will be obtained in the supine position, after the subject has been resting supine for at least 10 minutes. ECGs will be 12 lead with a 10 second rhythm strip. ECGs should be obtained prior to drawing blood samples. With the exception of Visit 3 ECG, all attempts should be made to use the same ECG recorder for all visits within individual subjects.

If a baseline measurement value is missing, change from baseline will be missing as well. For each summary, the number of non-missing observations, mean, median, standard deviation, minimum, and maximum will be presented by treatment group for both the actual and change from baseline values. The ECG parameters to be summarized include: heart rate, PR interval, QRS interval, QT interval, and QTc interval. QTc interval will be calculated using both Bazett ($\text{QTcB} = \text{QT} / (\text{RR})^{1/2}$) and Frederica's ($\text{QTcF} = \text{QT} / (\text{RR})^{1/3}$) corrections; if RR is not available, it will be replaced with 60/HR in the correction formula. In addition, the number and percentage of subjects by maximum on-treatment value of QTc/QTcB/QTcF intervals, categorized as Males: > 450 msec; Females: > 470 msec; > 450 msec and ≤ 480 msec; > 480 msec and ≤ 500 msec; and > 500 msec; maximum on-treatment change from baseline value of QTcB/QTcF intervals, categorized as > 30 msec and ≤ 60 msec, and > 60 msec; as well as increase in PR interval from baseline $> 25\%$ or a PR interval > 200 msec; increase in QRS interval from baseline $> 25\%$ or a QRS interval > 120 msec; decrease in HR from baseline $> 25\%$ or a HR < 50 bpm; and increase in HR from baseline $> 25\%$ or a HR > 100 bpm will be provided. All ECG data collected will be listed.

10.7. PHYSICAL EXAMINATION

A complete physical examination will be performed (including a genital/rectal exam if clinically indicated). Any clinically significant abnormality at Screening will be recorded on the Medical History form. Any new or worsening clinically significant abnormality at all other visits will be recorded on the Adverse Event form.

The data will be presented in the corresponding medical history and AE results, so no physical examination data summary and data listing will be presented.

10.8. PHYSIOTHERAPY

Subjects will be instructed on of a set of exercises (cylinder grasp, thumb raise, stand and squat, walk) to be carried out at home every morning and afternoon for the first six

INC1005439

Sponsor: San-Bio, Inc.

Protocol: SB-STR02

Final 1.0

Statistical Analysis Plan

months of the study, Screening (Visit 1) through Month 6 (Visit 8). Subjects will be asked to keep a daily diary of their performance of the exercises for the completing 30 repetitions.

Data will be summarized for at least 80% compliance of all tasks by visit and 80% compliance for all visits. Data listings will also be provided.

Statistical Analysis Plan

11. EXPLORATORY ANALYSIS

11.1. MRI

The following exploratory endpoints will be summarized.

Magnetic Resonance Imaging (MRI) of the brain will be obtained using either a 1.5 or 3 Tesla MRI scanner. Each subject should have all scans conducted on the same scanner if possible (excepting those used for stereotactic planning and post-operative assessments, within 2 weeks of the surgery (implant/sham)). Standard T1 and T2 sequences and FLAIR will be obtained, and will be recorded in standard digital format for review. Contrast is to be utilized for MRI procedures at Baseline (Visit 2), Day of surgery (Visit 3B), Day 8 (Visit 5), Month 1 (Visit 6), and Month 12 (Visit 10); all other scheduled MRI to be performed without contrast. MRI within 3 months of Visit 1 is acceptable for Screening MRI.

Diffusion tensor imaging (DTI) is an MRI technique which characterizes the magnitude, anisotropy and orientation of the diffusion tensor, using the pulsed-gradient, spin echo pulse sequence with a single-shot, echo planar imaging readout. DTI data will be obtained using whole brain coverage, a maximum of 2.5 mm isotropic resolution and at least 30 diffusion encoding directions and may be obtained using either a 1.5 or 3 Tesla MRI scanner. DTI is required for subjects at assessment sites with DTI capability. DTI is optional for sites without access to DTI-compatible scanners. Perfusion imaging, including Dynamic Susceptibility Contrast (DSC), is also required for subjects at assessment sites when the MRI has the capacity. A centralized imaging core laboratory will be used to review lesion size selection criteria at study entry, develop imaging acquisition protocols, and conduct imaging processing and analyses.

The primary analyses of the primary efficacy endpoint and the analyses of the head MRI variables will be performed on the following head MRI subgroups of interest:

- Presence of FLAIR lesion at Day 8
- Presence of enhancing lesion at Day 8
- Location of FLAIR lesion at Day 8

For the purposes of this SAP, when a subject has more than one FLAIR lesion, then the location will be based on the largest lesion. It is recognized that these subgroup variables are measured post-treatment, so they may well be affected by the treatment, but there is interest in the relationship between these variables and the primary efficacy endpoint because it may help to explain what is happening biologically.

INC1005439

Sponsor: San-Bio, Inc.

Protocol: SB-STR02

Final 1.0

Statistical Analysis Plan

Scatter plots between the change from baseline in the FMMS score at Month 6 and the change from baseline in each head MRI variable will be presented overall and for the MRI subgroups.

For the pooled SB623 versus sham surgery treatment groups, descriptive statistics will be presented by visit for the actual values and the changes from baseline for each head MRI variable. Analyses will be performed overall and for the head MRI subgroups specified above.

The numbers and percentages of subjects with FLAIR lesion at Day 8 and with enhancing lesion at Day 8 will be presented by treatment group. Descriptive statistics will be presented for maximum diameter of FLAIR lesion at Day 8, and the x, y, and z dimensions of FLAIR lesion at Day 8. The number and percentage of subjects will be presented for each FLAIR lesion location at Day 8.subject

All MRI and DTI results will be provided in data listings, as appropriate.

11.2. LEG ACTIVITY MONITORING

The following variables from Leg Activity Monitoring will be analyzed.

- Average Daily Total Energy Expenditure (affected side and non-affected side separately)
- Average Daily Activity Counts (affected side and non-affected side separately)
- Average Non-Sedentary Time per Day (affected side)
- Average Time of Moderate or Vigorous Activity per Day (affected side)

For the first two endpoints listed above, the value of the endpoint will be calculated as follows. The mean of each day's value will be calculated for the two-week period prior to Baseline, which will be the baseline value for this endpoint, and for the two-week period prior to each study visit.

Average Non-Sedentary Time per Day: The leg activity monitor can measure the time in minutes within each activity range. Activity range is categorized as sedentary, light, moderate, or vigorous based on energy expenditure. The light, moderate, and vigorous activity ranges are considered non-sedentary. The mean of each day's time within the non-sedentary range will then be obtained for the two-week period prior to Baseline, which will be the baseline value for this endpoint, and for the two-week period prior to each study visit.

Average Time of Moderate or Vigorous Activity per Day: The leg activity monitor can

INC1005439

Sponsor: San-Bio, Inc.

Protocol: SB-STR02

Final 1.0

Statistical Analysis Plan

measure the total amount of time in minutes within the moderate or vigorous activity ranges throughout each day. The mean of each day's value will then be calculated for the two-week period prior to Baseline, which will be the baseline value for this endpoint, and for the two-week period prior to each study visit.

For the pooled SB623 and sham surgery treatment groups, descriptive statistics will be presented by visit for the actual values and the changes from baseline for each leg activity monitoring variable.

Every effort will be made to minimize the number of dropouts and to document reasons for dropping out. The following rules will be followed for missing leg activity monitoring data:

- If there are 5 or less daily values are missing within the 2-week period, then the missing daily values within a 2-week period will be imputed as the mean of the non-missing daily values for the period.
- If there are more than 5 daily values are missing for a 2-week period, the Last-Observation-Carried-Forward (LOCF) method (i.e. the last 2-week period with 5 or less non-missing daily values) will be used to impute the value for the 2-week period.

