15.12 Leg Activity Monitoring

Bilateral ankle sensors will be worn by subjects for 2 week intervals at Screening (Day -14), Baseline (Day -1) and Months 1, 3, 6, and 9. Data will be provided to a centralized reviewer for analysis. Detailed information regarding leg activity monitoring will be provided separately from this protocol.

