4.3. EXPLORATORY ENDPOINTS

- Improvement by ≥ 6 points at Month 6 from Baseline in UE-FMMS score
- Improvement by ≥ 3 points at Month 6 from Baseline in LE-FMMS score
- Standard T1- and T2-weighted MRI
- Fluid-attenuated Inversion Recovery (FLAIR)
- Dynamic Susceptibility Contrast (DSC) imaging
- Diffusion Tensor Imaging (DTI) with tractography and perfusion imaging
- Motion of leg affected by stroke as measured by leg activity monitor

INC1005439

Sponsor: San-Bio, Inc.

Protocol: SB-STR02

Final 1.0

Statistical Analysis Plan

- Outcome analysis among all subjects based on genotyping of polymorphisms at 3 specific loci: HLA - degree of donor/recipient mismatch; BDNF Val66Met mutation present (yes/no); and ApoE (i.e., homo and heterozygosity for ApoE2, ApoE3, ApoE4 alleles)

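### The SAP's carry-forward rule for leg-activity periods says non-missing where it should say missing, so it can draw only on periods the SAP itself rejects

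*SAP*

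**What the plan says.** Protocol Section 15.12 sets the wear time: "Bilateral ankle sensors will be worn by subjects for 2 week intervals". SAP Section 11.2 averages the daily values over the two weeks before Baseline and "for the two-week period prior to each study visit". Each period is therefore 14 days.

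Section 11.2 then gives two rules for missing days.

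- **Rule 1.** "If there are 5 or less daily values are missing within the 2-week period", the gaps "will be imputed as the mean of the non-missing daily values for the period". The period is kept.
- **Rule 2.** "If there are more than 5 daily values are missing for a 2-week period", the period's value is imputed by LOCF. A parenthesis opening with 'i.e.' defines the period to carry forward as "the last 2-week period with 5 or less non-missing daily values".

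SAP Section 4.3 lists the endpoint as exploratory: "Motion of leg affected by stroke as measured by leg activity monitor". For pooled SB623 and sham, "descriptive statistics will be presented by visit for the actual values and the changes from baseline for each leg activity monitoring variable". Section 11.2 specifies no model, test or confidence interval for these variables.

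**The concern.** Rule 1 counts missing days and Rule 2's parenthesis counts non-missing days, both against a threshold of 5. In a 14-day period these are opposite conditions: 5 or fewer missing is a well-recorded period, and 5 or fewer non-missing is a sparse one. A carry-forward rule is meant to replace a poor period with an earlier good one. As written, it may only look back to poor ones.

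A programmer following the text would get no usable value, or one less reliable than the value being replaced. A programmer who guessed the intent would depart from a final SAP without a record. What is at stake is the leg-activity summary (Table 14.2.7.1) and the subject listing (Listing 16.2.6.7).

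**Working it through.** There is no computed figure in the plan to reproduce here; the item is a rule. The check is to list every possible period and see which condition it meets.

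**Inputs.** Period length D = 14 days (SAP 11.2; Protocol 15.12). Let v be the number of valid days and m = 14 − v the number missing.

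**Conditions, converted to valid days.**

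- Accepted under Rule 1: m ≤ 5, so v ≥ 14 − 5 = 9.
- Replaced under Rule 2: m > 5, so v ≤ 8.
- Eligible source as written: v ≤ 5, so m ≥ 9.

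| Valid days v | Missing days m | Accepted (m ≤ 5) | Needs LOCF (m > 5) | Source as written (v ≤ 5) | Source if the word is 'missing' (m ≤ 5) |
|---|---|---|---|---|---|
| 0–5 | 14–9 | no | yes | yes | no |
| 6–8 | 8–6 | no | yes | no | no |
| 9–14 | 5–0 | yes | no | no | yes |

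**Results.**

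1. The source set (0–5) and the accepted set (9–14) do not overlap.
2. The source set lies wholly inside the set that needs LOCF (0–8), so each source calls for its own replacement. That is the circularity.
3. A period with 6 to 8 valid days must be replaced but can only be replaced by one with 5 or fewer. A source with no valid days qualifies.
4. If all of a subject's earlier periods have 6 or more valid days, there is no eligible source and nothing is imputed.
5. With 'missing' in the parenthesis, the source set becomes 9–14, exactly the set Rule 1 accepts, and the two rules are complementary.

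**Could another period length reconcile the rules?** Both v ≤ 5 and D − v ≤ 5 require D ≤ 10. No 14-day period can meet both.

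**Precision of one subject's mean.** Assume that daily values are independent with equal variance; the documents give no information on this. The standard error of a mean of v days is then proportional to 1/√v.

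- 5 days against 9: √(9/5) = 1.34
- 5 days against 14: √(14/5) = 1.67

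These ratios cover day-to-day error within a subject only. The spread of subject means in a group also contains between-subject variance. As an illustration, set the between-subject variance and the single-day variance both to 1, so that the variance of a subject mean is 1 + 1/v:

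- 5 against 9 days: √((1 + 1/5)/(1 + 1/9)) = √(1.200/1.111) = 1.04
- 5 against 14 days: √((1 + 1/5)/(1 + 1/14)) = √(1.200/1.071) = 1.06

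Even these would apply only if every value in the group had been imputed.

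**Does any other text override the rule?** SAP 7.2.3 defines Month 6 and Month 12 LOCF endpoints but sets no condition on daily values. SAP 7.3.2 covers FMMS, NeuroQOL and the other secondary endpoints, not the monitor. Protocol 15.12 and 18.5 give no imputation rule for it. The FMMS total-score rule in SAP 7.3.2 uses the same threshold in the expected direction: up to 5 missing items can be filled, more than 5 cannot. That points to a slip in one word.

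**The case against.** The best case on the other side is that this is a typing slip with an obvious meaning. The threshold of 5 is mirrored from Rule 1, the literal rule is circular, and a competent programmer would query it rather than produce poor values in silence. The variables are exploratory and only described. The documents give no estimate of how often a period will lack more than 5 days, so the rule may seldom be used.

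All of that stands, and it limits the importance of the point. It does not remove the error: the sentence is an operative imputation rule in a SAP marked final, and no other section corrects it.

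A reader might go further in three ways that the documents do not support.

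- **That the trial's only objective activity measure is compromised.** Protocol Section 20.4 describes gait velocity as objective, and Section 20.0 lists gait velocity and ARAT under disability or activity; both are secondary endpoints. The monitor is a device-based measure of daily leg motion, not the only objective one.
- **That the reported values will be means of 1 to 5 days, with errors up to √14 = 3.74 times larger.** A source with no valid days also qualifies, and each source itself triggers Rule 2, so the literal outcome is not defined as a short mean. The ratio also ignores between-subject variance.
- **That the efficacy conclusions are at risk.** Neither the primary analysis nor any secondary analysis in SAP Section 9 uses leg-activity data.

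**Conclusion.** The rule is wrong as written. For a 14-day period this is certain and needs no assumption: the permitted sources have 0 to 5 valid days, the accepted periods have 9 to 14, and the two never meet. That the drafter meant 'missing' is an inference, though a strong one, because that single change makes the two rules fit exactly.

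The consequence is small. It is confined to the exploratory leg-activity variables of SAP Section 11.2 and their table and listing. The factor of 1.3 to 1.7 for a 5-day mean rests on independent days and describes one subject's day-to-day error. The effect on group summaries would be smaller. It cannot be computed, because the documents give neither the variance components nor the frequency of sparse periods. This is a drafting correction worth making, not a threat to the trial's conclusions.

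**What to change.** In the parenthesis of the second missing-data rule in SAP Section 11.2, change 'non-missing' to 'missing', so that the source is the most recent two-week period with 5 or fewer missing daily values. The cost is one word, with no new data and no change to any other analysis. It should be made before unblinding, or, if the SAP can no longer be amended, recorded as a correction in the study report.

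The correction need not settle whether the Baseline period may serve as a source. Section 11.2 is silent on this. Section 7.2.3 limits the Month 6 and Month 12 LOCF endpoints to post-baseline assessments, and extending that limit to the monitor would leave the first post-baseline period without a source. That is a separate choice for the sponsor.
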